A recent study by Christenson et al studying patients with preeclampsia on aspirin prevention found that prenatal aspirin use was associated with a decreased incidence of postpartum hypertension within 48 hours after delivery and decreased rates of 6-week hospital readmission.¹⁹ Currently, there is no known role for continuation of aspirin in the postpartum period in at-risk patients and studies on the subject are limited.

While there are no definitive serum markers that can predict or diagnose preeclampsia, several have been studied as diagnostic tools. B-type natriuretic peptide (BNP) and N-terminal pro B-type natriuretic peptide (NT-proBNP) are included. Resnik et al studied B-type natriuretic peptide (BNP) levels in 118 pregnant patients from first trimester to term gestation. In this study, patients with preeclampsia with severe features had significantly higher BNP levels than both patients with preeclampsia without severe features ($P<0.01$) or patients without hypertensive disorders of pregnancy (<0.01). They established a BNP cut-off of <40.6 as having a negative predictive value of 92% in excluding preeclampsia during pregnancy.²⁰ A 2013 systematic review supported this conclusion and found that patients with preeclampsia had significantly higher BNP in the third trimester, which was thought to be indicative of cardiovascular dysfunction associated with preeclampsia.²¹ Additionally, BNP and NT-proBNP are currently widely used biomarkers for the diagnosis of heart failure and cardiovascular disease and risk-stratification for cardiovascular disease and long-term morbidity and mortality outside of pregnancy.²²⁻²⁴

Notably, however, there is no established “normal” BNP or NT-proBNP level during pregnancy or postpartum. Denoble et al compared NT-proBNP levels between obese and non-obese women throughout pregnancy at our institution and found that while NT-proBNP levels were lower in obese subjects during pregnancy, the difference was not significant in the postpartum setting.²⁵ In this study, the postpartum NT-proBNP in the obese population was 33 (27-56) and non-obese population was 23 (8-42).²⁵ Finally, Sheikh et al performed a meta-analysis of available literature on BNP and NT-proBNP levels during pregnancy and postpartum and found that both biomarkers are useful diagnostic tools for cardiac complications in both pregnant and recently delivered patients.²⁶

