This is a randomized-controlled trial of comparing NT-proBNP levels at 4-6 weeks postpartum between patients randomized to continuation of postpartum aspirin 81 mg for 6 weeks postpartum and placebo. Patients meeting inclusion criteria will be approached during routine prenatal visits, on arrival to Labor and Delivery, or following delivery for enrollment. Informed consent will be obtained, and patients will be randomized in a 1:1 fashion to aspirin 81 mg vs identical-appearing placebo to be continued for 6 weeks' postpartum. Patients will receive these medications prior to hospital discharge. Patients will be scheduled for routine postpartum follow-up appointment at 4-6 weeks as is standard of care at Duke. Patients will be reminded of their appointment via telephone call or text message the day prior to their scheduled follow-up visit. NT-proBNP levels will be drawn at the 4-6-week postpartum visit. This will be one blood draw with a total of 10 mL collected. NT-proBNP levels will be compared between groups.

Patients will be eligible for randomization if they are 18 years of age or older, English-speaking, postpartum, have met USPSTF recommendations for low-dose aspirin use during pregnancy: ≥ 1 high risk factor (history of preeclampsia in prior pregnancy, multifetal gestational, chronic hypertension, preexisting diabetes, renal disease, autoimmune disease) or ≥ 2 moderate risk factors (nulliparity, obesity, family history of preeclampsia, sociodemographic characteristics, age 35 years or older, or personal history factors) and reported at least 50% compliance with aspirin during pregnancy. Patients will be excluded if they have had a hypersensitivity reaction to aspirin or other salicylates, history of gastrointestinal bleeding, history of gastric or duodenal ulcers, severe hepatic dysfunction, bleeding disorders and diathesis, known cardiac dysfunction with reduced ejection fraction, or are taking or prescribed ACE inhibitors. Patients requiring ICU admission during their pregnancy will be excluded.

Patients will be randomized in a 1:1 fashion to aspirin 81 mg vs identical-appearing placebo to be continued for 6 weeks' postpartum using a block randomization scheme implemented in RedCap.

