Baseline characteristics will be summarized by control and intervention group. Continuous variables will be summarized using mean (standard deviation) or median (25th percentile, 75th percentile) while categorical variables will be summarized using frequency (percentage). Primary outcome, NT-proBNP levels at 4-6 weeks postpartum, will be summarized and compared between groups using two-sample t-test or Wilcoxon rank sum test, depending on the empirical distribution of the data. Secondary outcomes will be compared between groups using the chi-square, Fisher's exact, Mann Whitney U, or student's t-tests, as appropriate. A p-value of M0.05 will be considered significant. Analyses will be performed in R 4.2.0 (R Core Team, 2022) or SAS 9.4 (SAS Institute Inc., Cary, NC).

A prior study at our institution found the following NT-proBNP levels in patients with and without obesity at 4-6 weeks postpartum:

NT-proBNP at 4-6 weeks postpartum	
Mean (SD)	37.4 (32.2)
Median	30.5
Q1, Q3	11.0, 47.0
Range	(2.5-135.0)

Using this mean and standard deviation with a target power of 0.8 at 0.05 level of significance, we calculated a sample size of 90 to detect a medium effect size (Cohen's d = 0.6), which is equivalent to a difference of 19.3 between control and intervention. To account for a 20% drop-out rate, we calculated a sample size of 114 (57 in each group).

This study is designed to be performed within a 24-month timeframe. Patient enrollment will start in spring 2023. Trained research staff will enroll patients in the clinic, on Labor and Delivery and postpartum with the goal to meet our sample size for enrollment by spring 2024.

Data & Safety Monitoring

- Summarize safety concerns, and describe the methods to monitor research subjects and their data to ensure their safety, including who will monitor the data, and the frequency of such monitoring. If a data monitoring committee will be used, describe its operation, including stopping rules and frequency of review, and if it is independent of the sponsor (per 45 CFR 46.111(a) (6)).

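### The plan neither stratifies by nor adjusts for preeclampsia in the index pregnancy, so it gives up some precision and has no prespecified response to a visible imbalance

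*Combined protocol and SAP*

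**What the plan says.** Design & Procedures describes 1:1 allocation "using a block randomization scheme implemented in RedCap" and names no stratum. Women must be postpartum to be eligible for randomisation, and they receive study drug before discharge. The only blood draw is at the 4-6 week visit, so there is no baseline NT-proBNP.

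Eligibility rests on risk factors for preeclampsia, including preeclampsia in a prior pregnancy. Preeclampsia in the current pregnancy is neither an inclusion nor an exclusion criterion. A postpartum diagnosis of preeclampsia is listed as a secondary outcome.

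Under Data Analysis & Statistical Considerations, the primary outcome is "compared between groups using two-sample t-test or Wilcoxon rank sum test, depending on the empirical distribution of the data". Baseline data are handled descriptively: "Baseline characteristics will be summarized by control and intervention group". No covariate, adjusted model or sensitivity analysis is mentioned.

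Background & Significance cites a study in which "patients with preeclampsia with severe features had significantly higher BNP levels than both patients with preeclampsia without severe features" or no hypertensive disorder, and a systematic review reporting higher third-trimester BNP in preeclampsia.

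**The concern.** The trial will mix women who had preeclampsia in this pregnancy with women who did not. If the association described in the background lasts into the 4-6 week window, part of the spread in the primary endpoint comes from a factor that is knowable at randomisation and that the analysis ignores. With a single post-treatment measurement, nothing else in the plan absorbs it.

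Two things are at stake. The first is precision, because variation that could be explained stays in the error term. The second is interpretation. If the baseline table shows clearly more preeclampsia in one arm, the plan does not say what to do, and any adjustment made then would be post hoc and open to challenge.

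**Working it through.** **Inputs from the documents.** SD 32.2, target difference 19.3, d = 0.6, power 0.80, alpha 0.05 (taken as two-sided), 90 evaluable (45 per arm), 20% drop-out, 114 enrolled.

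**Assumptions, because the documents give neither figure.** Prevalence p of index-pregnancy preeclampsia is 20-40%. Its effect D on 4-6 week NT-proBNP is 0.2, 0.5 or 1 SD, that is 6.4, 16.1 or 32.2 units. Total SD is held at 32.2.

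**Step 1: reproduce the plan.** 0.6 × 32.2 = 19.32. The exact t-test solution for d = 0.6 is 44.6, so 45 per arm and 90 in all, with power 0.804. For drop-out, 45/0.8 = 56.25, so 57 per arm and 114 in all. The stated sizes reproduce.

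**Step 2: chance imbalance.** The SD of the between-arm difference in prevalence is sqrt(2p(1−p)/45), which is 0.084, 0.097 and 0.103 for p = 0.2, 0.3 and 0.4. From exact binomials, the arms differ by 5 or more women with probability 0.23, 0.30 and 0.33.

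**Step 3: shift and power.** The 95% shift is 1.96 × sqrt(2p(1−p)/45) × D. The share of variance explained is R² = p(1−p)D²/32.2². Adjusted power uses d = 0.6/sqrt(1−R²) in the same t-test calculation.

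| Effect of preeclampsia | 95% shift, p = 0.2 to 0.4 | Share of 19.3 | R² | Adjusted power |
|---|---|---|---|---|
| 0.2 SD | 1.1 to 1.3 | 6-7% | 0.006-0.010 | 0.81 |
| 0.5 SD | 2.7 to 3.3 | 14-17% | 0.04-0.06 | 0.82-0.83 |
| 1 SD | 5.3 to 6.5 | 28-34% | 0.16-0.24 | 0.87-0.90 |

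An imbalance of exactly 5 women moves the estimate by 5/45 × D: 0.7 units at 0.2 SD, 1.8 at 0.5 SD and 3.6 at 1 SD (4%, 9% and 19% of 19.3).

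**Step 4: comparison with total sampling error.** The standard error of the difference is 32.2 × sqrt(2/45) = 6.79, so its 95% range is ±13.3 units. The shifts in step 3 are a component of that range and do not add to it.

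**Step 5: validity.** In simulation with p = 0.3, D = 40 and total SD 32.2 (R² = 0.32, above the range in the table), overall type I error of the unadjusted t-test was 0.050. It was 0.147 in the 13% of trials with an imbalance of 15 points or more, and 0.022 when the imbalance was under 5 points. With an effect of 1 SD it was about 0.09 when the arms differed by 5 or more women. With 0.5 SD it was about 0.06.

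**Step 6: if the planning SD is too small.** The 32.2 comes from patients described by obesity, with no preeclampsia share given. If preeclampsia adds variance to it (p = 0.3, normal approximation), D = 30 gives SD sqrt(32.2² + 0.21 × 30²) = 35.0 and unadjusted power 0.74. D = 50 gives SD 39.5 and power 0.64. Adjustment restores about 0.81 in both cases.

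**The case against.** Unstratified blocks with an unadjusted comparison form a valid design. Chance imbalance is part of the sampling error that the standard error already measures, and if 32.2 is the right total SD the planned sample size already allows for it. That stands.

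The prognostic premise is also thin. The cited findings concern BNP during pregnancy, with no size given and nothing on NT-proBNP at 4-6 weeks. If the effect has largely resolved by then (0.2 SD), the power gain is negligible. The exclusions for ICU care and known reduced ejection fraction may also remove some of the more extreme cardiac cases. These points limit the size of the concern, but they do not give a reason to leave the factor out.

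A reader might infer that imbalance could imitate or hide much of the target difference, or that it biases the trial. The documents support neither. For p of 20-40%, moving the estimate by half of 19.3 at the 95% imbalance needs D of about 48 to 58 units, above the overall planning mean of 37.4. At total SD 32.2 the full target is out of reach at that imbalance. The type I error inflation in step 5 applies only within the subset of trials with a large imbalance.

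A reader might also want obesity as a required covariate, given the postpartum values of 33 and 23 in Background & Significance. The same paragraph reports that postpartum difference as not significant.

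**Conclusion.** The point holds as an inexpensive improvement in precision and prespecification, not as a threat to validity. The plan leaves out a plausible prognostic factor that can be recorded before randomisation, and it has no rule for a visible imbalance. Under the assumed ranges, the 95% chance shift is about 1 to 6.5 units (6-34% of 19.3), and power at 45 per arm rises from 0.80 to about 0.81-0.90.

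The result depends on assumed prevalence and effect size, and on persistence to 4-6 weeks that the documents do not establish. The power figures are on the raw scale. The gain on the log scale depends on the R² there, which cannot be calculated from the documents.

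**What to change.** In Data Analysis & Statistical Considerations, make the primary comparison a prespecified linear model of log NT-proBNP on arm, adjusted for index-pregnancy preeclampsia (yes/no). Count only diagnoses made before randomisation, because a later diagnosis is a secondary outcome and could be affected by treatment. The log scale suits planning data that look right-skewed (mean 37.4, median 30.5, range 2.5-135.0). Keep the Wilcoxon test as a sensitivity analysis.

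If enrolment has not begun, also make that factor a stratum in the REDCap block scheme. If it has begun, leave the allocation list alone and rely on the model. BMI or obesity is at most an optional second covariate.

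The cost is about one degree of freedom, one stratum field and a short change to the analysis text, with no extra patients or blood draws. The effect would be reported as a ratio of geometric means rather than a difference in units. If preeclampsia proves weakly prognostic at 4-6 weeks, little is gained.

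Suggested wording: *The primary analysis will be a linear model of log-transformed NT-proBNP at 4-6 weeks on randomised arm, adjusted for preeclampsia in the index pregnancy diagnosed before randomisation (yes/no), reported as a ratio of geometric means with a 95% confidence interval. An unadjusted Wilcoxon rank sum test will be a sensitivity analysis.*

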***Please enter the Short Title you would like to use to reference the study:**

Postpartum ASA and NT-proBNP

* This field allows you to enter an abbreviated version of the Study Title to quickly identify this study.

Standard Research Summary

Purpose of the Study

- Objectives & hypotheses to be tested

Specific Aim 1: To compare NT-proBNP levels at 4-6 weeks postpartum between patients continued on 6 weeks of aspirin use postpartum and placebo.

Our hypothesis is that NT-proBNP levels will be lower in the group randomized to continuation of aspirin for 6 weeks' postpartum. As we know that aspirin use during pregnancy decreases preeclampsia risk and that preeclampsia in itself is a risk factor for long-term cardiovascular disease in our patient population, we anticipate that the continuation of aspirin in the postpartum setting decreases cardiac strain and that patients continued on maintenance aspirin dosing will have lower NT-proBNP levels at 4-6 weeks postpartum.

Specific Aim 2: To compare average blood pressure readings at the 4-6 week postpartum visits as well as hospital readmission rates for blood pressure monitoring or cardiovascular concerns in the 4-6 week postpartum period between groups.

We plan to evaluate if patients continued on aspirin for 6 weeks postpartum have lower hospital readmission rates than patients on placebo. This could support prior data that showed that prenatal aspirin use was associated with decreased incidence of postpartum hypertension following delivery and decreased rates of hospital readmission.

Background & Significance

- Should support the scientific aims of the research

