The primary outcome for this analysis will be 4-6 week postpartum NT-proBNP levels. Secondary outcomes will be rates of preeclampsia diagnosis postpartum, rates of eclampsia, hospital readmission rates for blood pressure monitoring or cardiovascular disease work-up indications, number of subjects requiring initiation or increase in blood pressure medications, hospital readmission rates for bleeding-related complications, and rates of blood transfusions.

Selection of Subjects

- List inclusion/exclusion criteria and how subjects will be identified.

Patients will be eligible for randomization if they are 18 years of age and older, English-speaking, postpartum, have met USPSTF recommendations for low-dose aspirin use during pregnancy: ≥ 1 high risk factor (history of preeclampsia in prior pregnancy, multifetal gestational, chronic hypertension, preexisting diabetes, renal disease, autoimmune disease) or ≥ 2 moderate risk factors (nulliparity, obesity, family history of preeclampsia, sociodemographic characteristics, age 35 years or older, or personal history factors) and reported at least 50% compliance with aspirin during pregnancy.

Patients will be excluded if they have had a hypersensitivity reaction to aspirin or other salicylates, history of gastrointestinal bleeding, history of gastric or duodenal ulcers, severe hepatic dysfunction, bleeding disorders and diathesis, known cardiac dysfunction with reduced ejection fraction, or are taking or prescribed ACE inhibitors. Patients who required ICU level care during their pregnancy will be excluded.

Subject Recruitment and Compensation

- Describe recruitment procedures, including who will introduce the study to potential subjects. Describe how you will ensure that subject selection is equitable and all relevant demographic groups have access to study participation (per 45 CFR 46.111(a) (3)). Include information about approximately how many DUHS subjects will be recruited. If subjects are to be compensated, provide specific prorated amounts to be provided for expenses such as travel and/or lost wages, and/or for inducement to participate.

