Patients will be approached for enrollment based on their eligibility in clinic, on admission to Labor and Delivery, or following delivery at Duke University. All patients who deliver at Duke University Hospital will be eligible for screening. Study staff will approach the subject and provide information regarding the study. If the patient is interested in participating, then study staff will obtain informed consent at that time.

The total goal enrollment is 114 participants (57 in each group). Patients will receive a \$10 dollar gift certificate at their postpartum visit for participation in our study.

Subject's Capacity to Give Legally Effective Consent

- If subjects who do not have the capacity to give legally effective consent are included, describe how diminished capacity will be assessed. Will a periodic reassessment occur? If so, when? Will the subject be consented if the decisional capacity improves?

We will not be including patients that do not have the capacity to give legally effective consent.

Study Interventions

- If not already presented in #4 above, describe study-related treatment or use of an investigational drug or biologic (with dosages), or device, or use of another form of intervention (i.e., either physical procedures or manipulation of the subject or the subject's environment) for research purposes.

The treatment group will be provided with a 6-week supply of 81 mg of aspirin prior to discharge from the delivery admission. The control group will receive a 6-week supply of placebo medication from the Investigational Pharmacy prior to discharge. The placebo will be identically appearing to the 81 mg aspirin. Patients will be scheduled for a 4-6 week postpartum clinic appointment, which is standard for these patients outside of this proposal.

Risk/Benefit Assessment

- Include a thorough description of how risks and discomforts will be minimized (per 45 CFR 46.111(a) (1 and 2)). Consider physical, psychological, legal, economic and social risks as applicable. If vulnerable populations are to be included (such as children, pregnant individuals, imprisoned persons or cognitively impaired adults), what special precautions will be used to minimize risks to these subjects? Also identify what available alternatives the person has if he/she chooses not to participate in the study. Describe the possible benefits to the subject. What is the importance of the knowledge expected to result from the research?

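### Does the missing blood pressure outcome, or the lack of a counting start for the event outcomes, call for a change to the secondary outcomes?

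*Combined protocol and SAP*

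**What the plan says.** All references are to the combined protocol and SAP.

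- **Purpose of the Study, Specific Aim 2** sets out "To compare average blood pressure readings at the 4-6 week postpartum visits as well as hospital readmission rates". The readmissions are those for blood pressure or cardiovascular reasons, compared "in the 4-6 week postpartum period between groups".
- **Design & Procedures** lists six secondary outcomes. It begins "Secondary outcomes will be rates of preeclampsia diagnosis postpartum, rates of eclampsia, hospital readmission rates for blood pressure monitoring" (extended to cardiovascular work-up) and ends with "number of subjects requiring initiation or increase in blood pressure medications, hospital readmission rates for bleeding-related complications, and rates of blood transfusions". No blood pressure reading is among the six.
- **Design & Procedures**, on timing: "Patients will be eligible for randomization if they are 18 years of age or older, English-speaking, postpartum". Consent may come earlier, but randomisation may not. Preeclampsia in the index pregnancy is not an exclusion.
- **Study Interventions**: "The treatment group will be provided with a 6-week supply of 81 mg of aspirin prior to discharge from the delivery admission". Placebo is supplied at the same point.
- **Data Analysis & Statistical Considerations**: "Secondary outcomes will be compared between groups using the chi-square, Fisher's exact, Mann Whitney U, or student's t-tests, as appropriate".

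**The concern.** Two things catch the eye.

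First, an aim and the outcome list disagree. Half of Aim 2 is a continuous blood pressure comparison, and the list does not carry it. The analysis section names t-tests and Mann-Whitney tests for secondary outcomes, yet all six listed items are rates or counts of subjects. A continuous outcome seems to have been intended and left off.

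Second, there is an interval between delivery and randomisation. Eclampsia, starting or increasing blood pressure medication, and transfusion carry no time reference. Preeclampsia is dated only as postpartum, which begins at delivery and therefore before randomisation. Read literally, an event in that interval could be counted although allocation cannot have influenced it. Such events would be expected to pull the risk ratio towards 1, for a benefit (preeclampsia, medication) and for a harm (transfusion). The harm side deserves attention, because transfusion is one of only two listed bleeding outcomes.

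**Working it through.** **The plan's own figure.** Inputs from Data Analysis & Statistical Considerations: SD 32.2, d = 0.6, power 0.80, alpha 0.05 (taken as two-sided), drop-out 20%. The difference is 0.6 × 32.2 = 19.3. A two-sample t-test needs 44.59, so 45 per arm, or 90 in total. Drop-out: 45 / 0.8 = 56.25, so 57 per arm, or 114. The stated sizes reproduce, and no secondary outcome enters them.

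**Part 1, passages side by side.**

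| Needed for the analysis | Where it stands |
|---|---|
| Measure: average blood pressure | Specific Aim 2 |
| Time: 4-6 week visit | Specific Aim 2 |
| Contrast: between groups | Specific Aim 2 |
| Test: t-test or Mann-Whitney | Data Analysis & Statistical Considerations |
| Entry in the secondary list | Absent |

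Only the list entry is missing. A statistician working from the whole document would run the comparison.

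**Part 2, which outcomes are exposed.** Study drug is supplied before discharge, so both readmission outcomes can only occur after randomisation. Preeclampsia has a start (delivery) that is slightly too early. Eclampsia, medication change and transfusion have none. The interval at issue lies within the delivery admission.

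**Part 2, size.** The documents give no secondary event rates, so every input below is assumed. Let p be the risk after randomisation, and q the share with an event before it, equal in both arms.

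Observed risk = q + (1 − q) × p.

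*Preeclampsia*, p = 0.12 on placebo and 0.06 on aspirin, true risk ratio 0.50. Power uses the unpooled z-test, two-sided 0.05, 57 per arm.

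| q | Placebo | Aspirin | Risk ratio | Power, earlier cases counted | Power, earlier cases left out |
|---|---|---|---|---|---|
| 0 | 0.120 | 0.060 | 0.50 | 20.3% | 20.3% |
| 0.01 | 0.129 | 0.069 | 0.54 | 18.7% | 20.1% |
| 0.05 | 0.164 | 0.107 | 0.65 | 14.5% | 19.5% |

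For example, q = 0.05 gives 0.05 + 0.95 × 0.12 = 0.164 and 0.05 + 0.95 × 0.06 = 0.107, so the ratio is 0.107 / 0.164 = 0.65.

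A much larger dilution appears only if every woman diagnosed before delivery is also counted. With q = 0.20 to 0.40 the ratio is 0.248 / 0.296 = 0.84 to 0.436 / 0.472 = 0.92. An antepartum diagnosis is not, on the ordinary reading, a postpartum one, so the listed outcome does not invite this. If those women stay in the denominator as non-events, the ratio is (1 − q) × 0.06 / [(1 − q) × 0.12] = 0.50, unchanged.

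*Transfusion*, p = 0.02 on aspirin and 0.01 on placebo, true risk ratio 2.0. With q = 0.02: 0.0396 / 0.0298 = 1.33. With q = 0.05: 0.0690 / 0.0595 = 1.16. Expected events after randomisation are 57 × 0.02 = 1.1 and 57 × 0.01 = 0.6 per arm.

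**The case for a change.** The strongest case for a change is that these definitions cost little to write, and that settling them before unblinded data are seen removes analyst discretion. The trial recruits women at risk of preeclampsia and does not exclude those who already had it in the index pregnancy, so earlier cases will probably be present. A transfusion at delivery would precede allocation, and counting it could blur a bleeding signal.

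Much of this stands as description. The list does omit the blood pressure reading, and no event outcome is tied to randomisation. It is also true that the plan does not say which readings make up the average, against which regimen a medication increase is judged, or when event counting ends outside the Aim 2 readmission window.

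What does not follow is that the plan as written leads to a wrong analysis. The text leaves the start open and does not direct anyone to count earlier events. Randomisation is the natural origin in a randomised comparison, and a diagnosis before it belongs with the baseline characteristics, which the plan already summarises by group. On transfusion the relative dilution could be marked, but at the assumed risks about one event per arm or fewer is expected after randomisation. No choice of start point makes that comparison informative at this sample size. The other bleeding outcome, readmission, is unaffected.

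**Conclusion.** No change is needed. The blood pressure omission is a clerical inconsistency between an aim and a list in the same short document, and the aim together with the named tests already specifies the comparison. The missing start point is a gap that analysts can fill sensibly by counting from randomisation.

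If it were filled badly, the effect would be confined to secondary outcomes and would be expected to act only towards no difference. On the ordinary reading of a postpartum diagnosis, the preeclampsia risk ratio would move from 0.50 to 0.54-0.65, and power would be low either way (about 14-19% against about 20%). For transfusion, a ratio of 2.0 would move to 1.33-1.16, on too few expected events to support a conclusion under either definition.

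These sizes rest on assumed risks (12% vs 6%; 2% vs 1%) and assumed shares with an earlier event (1-5%; 2-5%), equal in both arms and with all 57 per arm ascertained. The direction rests only on the fact that events before randomisation cannot depend on allocation. The primary outcome, its test and the sample size of 114 are untouched.

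### One 0.05 significance rule covers NT-proBNP and seven or eight secondary comparisons, with no adjustment, exploratory label or planned intervals

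*Combined protocol and SAP*

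**What the plan says.** Data Analysis & Statistical Considerations names a t-test or Wilcoxon test for NT-proBNP. It then says of the rest: "Secondary outcomes will be compared between groups using the chi-square", followed by Fisher's exact, Mann-Whitney and t-tests as alternatives. The next sentence is the only decision rule: "A p-value of M0.05 will be considered significant". The letter before 0.05 is read as a less-than or less-than-or-equal sign lost in text extraction and is not criticised.

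The secondary outcomes stand at the end of Design & Procedures: "Secondary outcomes will be rates of preeclampsia diagnosis postpartum, rates of eclampsia, hospital readmission rates for blood pressure monitoring" or cardiovascular work-up, then start or increase of blood pressure medication, readmission for bleeding, and transfusion. That is six. Specific Aim 2 has a further comparison that is not in that list: "To compare average blood pressure readings at the 4-6 week postpartum visits".

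Only NT-proBNP is powered, with a "target power of 0.8 at 0.05 level of significance". The document has no multiplicity adjustment, no order of testing among the secondary outcomes, no statement that they are exploratory, and no plan to report effect estimates or confidence intervals.

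**The concern.** Read as written, the plan lets any one of seven or eight secondary p-values be declared significant at 5%, whatever NT-proBNP shows. This matters because the primary outcome is a biomarker and the clinical outcomes are all secondary. Aim 2 is a declared aim, and its text proposes that lower readmission on aspirin could support earlier findings, so some inference from secondary results is intended.

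The same rule is uninformative in the other direction. Several of these outcomes may be rare in 114 women. A p-value above 0.05 for readmission, bleeding or transfusion could then be taken as absence of effect or as reassurance on safety, with no interval to show how much remains possible.

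**Working it through.** **1. The plan's own figure.** The inputs are SD 32.2, d = 0.6, power 0.80, alpha 0.05 and 20% drop-out, all from the analysis section. 0.6 × 32.2 = 19.32, the stated 19.3. A two-sided two-sample t-test needs 44.6 per arm, so 45 per arm and 90 in total. 45 / 0.8 = 56.25, so 57 per arm and 114 in total. The stated sample size reproduces, and it is for one comparison tested two-sided.

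**2. Number of secondary comparisons.** Six listed plus Aim 2 blood pressure gives 7. It is 8 if systolic and diastolic are tested separately, which is an assumption.

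**3. Independent tests, each at a full 5%, no true effect.** Chance of at least one p ≤ 0.05 = 1 − 0.95^k:

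| k | Chance |
|---|---|
| 6 | 26.5% |
| 7 | 30.2% |
| 8 | 33.7% |

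Counting the primary with eight secondaries gives 37.0% (k = 9), but the primary is a separate prespecified test.

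**4. Correlation.** With equal pairwise correlation between normal test statistics (simulated; the correlations are assumed):

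| Correlation | 7 tests | 8 tests |
|---|---|---|
| 0.3 | 27% | 30% |
| 0.5 | 23% | 25% |
| 0.8 | 15% | 16% |

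**5. Rare outcomes.** The documents give no event rates. Assumed ranges: eclampsia 0.1–0.5%, bleeding readmission 1–2%, transfusion 2–5%, postpartum preeclampsia 5–20%, blood pressure or cardiovascular readmission 5–15%, medication change 15–30%. The exact type I error of Fisher's test at 57 per arm is below 0.1% at rates of 2% or less, 1.0% at 5%, 2.1% at 10% and 3.2% at 30%.

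Low end: lowest rates, Fisher throughout, one blood pressure test at 5%. At 57 per arm, 1 − (0.9905 × 0.9905 × 0.9744 × 0.9994 × 0.95) = 9.3%; eclampsia and bleeding readmission contribute essentially nothing. At 45 per arm the figure is 8.5%.

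High end: highest rates, chi-square where the expected count per arm is at least 5 and Fisher elsewhere, two blood pressure tests at 5%. At 45 per arm, 1 − (0.9458 × 0.9452 × 0.9465 × 0.9998 × 0.9943 × 0.95²) = 24.1%.

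So the range is about 9% to 24%, still assuming independence.

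**6. What non-significance can show.** With 57 per arm, Fisher's test gives p = 0.057 for 5 events against 0 and p = 0.027 for 6 against 0, so at least six events are needed when the other arm has none. Exact power, with assumed placebo rates:

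| Placebo v aspirin | 57 per arm | 45 per arm |
|---|---|---|
| 5% v 0% | 6% | 2% |
| 10% v 0% | 51% | 29% |
| 15% v 0% | 87% | 69% |
| 10% v 5% | 8% | 6% |

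**The case against.** The strongest reply is that the plan does have a structure. It names one primary outcome, powers the trial on it alone and labels the rest secondary. In a single-centre biomarker trial of 114 women, many readers would discount unadjusted secondary p-values anyway. It is correct that the primary test keeps its 5% error. A reader might infer from the shared threshold that the primary result is compromised, but nothing in the documents supports that.

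Three further inferences also go too far.

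- A reader might take 34% as the expected error and call a chance finding likely. That figure needs eight independent tests each at a full 5%. Here some outcomes are probably too rare to contribute, and others overlap, such as systolic with diastolic pressure and eclampsia with preeclampsia. Even 34% is a minority probability, and it applies only if aspirin affects none of these outcomes.
- A reader might say that Aim 2 will treat a non-significant readmission result as the answer. The Aim 2 text says only that the question will be evaluated and that the result could support earlier data. It does not say how a null result will be read.
- A reader might conclude that the trial could never detect an effect on readmission. That depends on the unknown placebo rate: abolishing readmission has 6% power at 5% but 51% at 10%.

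There is also a fair warning about remedies. Bleeding readmission and transfusion are harm outcomes, where a missed signal is costly, so moving away from significance must not mean less reporting of them.

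What the reply leaves standing is that the only stated rule attaches the word significant to any secondary p-value that meets it, and nothing tells the reader how to weigh that.

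**Conclusion.** The concern holds as a matter of how secondary results may be claimed, not as a fault in the primary analysis. If aspirin affects none of the secondary outcomes, the chance of at least one significant secondary result is 30% (seven tests) or 34% (eight tests) with independent full-size tests. It is more plausibly about 9% to 24%, roughly two to five times the 5% that a single test suggests. The lower range rests on the assumed event rates, on the choice between Fisher and chi-square, on 45 to 57 women per arm, and on independence; positive correlation reduces it further.

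Non-significant results on rare outcomes are weak evidence in either direction. The clearest case is a halving from an assumed 10%, with 8% power at the full 57 per arm. The change is worth making because it alters what the trial may conclude about its clinical outcomes.

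**What to change.** In Data Analysis & Statistical Considerations, replace the single threshold with text such as:

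> *A two-sided p-value at or below 0.05 is the significance criterion for the primary outcome, NT-proBNP, only. Secondary outcomes, including those of Aim 2, are exploratory. Each is reported as a risk difference or mean difference with a 95% confidence interval. No significant benefit will be claimed from them, and no absence of effect or safety will be inferred from a non-significant result. Bleeding readmission and transfusion are reported in the same way and considered as possible safety signals.*

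In Design & Procedures, add visit blood pressure to the secondary outcome list so that it agrees with Aim 2, and say whether systolic and diastolic are analysed separately. The semi-annual safety review by the Data Monitoring Committee is unaffected.

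The cost is a few sentences, set before unblinding, with no extra women, data or loss of power for NT-proBNP. The downside is that a striking secondary result can no longer be called significant.
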